6.2 Status of the Subjects

The status of the subjects will be presented using a status dataset, Subject-Level Analysis Dataset (ADSL), that will be created and used throughout the tables and listings. This status dataset will contain information on the eligible, randomized, received study drug, completed, and reason for non-completion subjects. In addition, it contains the information for subjects in the all-treated, safety, immunogenicity, per-protocol, and the PD (exploratory) set.

6.3 Protocol Deviations

The Protocol Deviation list is a list that presents the deviations by subject, description of actual deviation and category (major or minor). The Protocol Deviation list will serve as input for the selection of subjects for inclusion in the per-protocol set. The Protocol Deviation list is created by

the Data Manager but may involve collaboration with the Biostatistician and/or the SAS programmer and is preferably based upon a predefined set of protocol deviations that is as inclusive as possible. The Protocol Deviation list will be discussed and agreed with the Sponsor at a mutual Protocol Deviation review meeting prior to DBL.

The deviation list will be finalized before Database Lock (DBL).

6.4 Creation and Documentation of Analysis Population

The Biostatistician will create an analysis population list indicating which subjects will be included in each analysis set as mentioned in Section 6.1 of the SAP.

This information will be presented in a Listing which is intended to be included in the Appendix of the Clinical Study Report.

7 REPORT SPECIFICATIONS AND STATISTICAL ANALYSES

7.1 General Considerations

For safety and tolerability analyses, the descriptive statistics presented will be frequency counts (n) and percentages for qualitative variables. Quantitative variables will be summarized using the number of available observations (n), mean, median, standard deviation (SD), minimum (min), and maximum (max) values.

For decimal display, appropriate rounding will be performed for all summary table: mean and median will be presented with one more decimal than the original data; SD will be presented with two more decimals than the original data; minimum and maximum values will be presented with the same precision as the original data. Percentages will be presented with 2 decimals and no decimals will be presented for integer value (For example, zero will be presented as 0 %).

Extra measurements (such as additional visits or repeat assessments) will not be included in the descriptive statistics but will be included in subject listings only.

For the calculation of baseline corrected values, baseline is defined the last value measured prior to (the first) study drug intake (vital signs, ECG, laboratory parameters, bile salt-stimulated lipase, C-reactive protein (CRP), erythrocyte sedimentation rate (ESR), and S-calprotectin and high sensitive CRP (hsCRP) (only RA patients)), unless otherwise specified. If no value prior to dosing is collected, the baseline value will be treated as missing for analysis.

For any results reported as above upper limit of quantification (>ULOQ), the numeric value for calculating summary statistics used to replace this label will be the ULOQ value, plus one unit of the smallest digit of the ULOQ number. For example, if the ULOQ is 2.3 units then the smallest digit is 0.3 and one unit greater at that decimal point would be 0.4. A ULOQ designation would then be replaced numerically as 2.3 + 0.1 or 2.4 units. Similarly, if the ULOQ was 20.3, then ">ULOQ" would be replaced by 20.4. In addition, for any results reported as below lower limit of quantification (<LLOQ), the numeric value used for this label will be the half of LLOQ value. For

example, if the LLOQ is 0.5 units then the final value for statistical summary will be the half of 0.5 which is a value 0.25 units. In case an >ULOQ or <LLOQ value will be replaced as described here (for the purpose of summarizing the data), this will be indicated in a footnote beneath the table.

All placebo subjects from the different cohorts at each part will be combined into a single group for summary purposes. Data will be summarized by treatment groups (dose levels and placebo). No statistical inference will be performed.

Note: some minor modifications may be necessary to the planned design of tables and listings to accommodate data collected during the actual study conduct. This is not considered a deviation from the preplanned statistical analysis.

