14. Prior to dosing and 4 hours post-dose.
15. 4 hours post-dose.

16. Up until study drug administration.
17. Spare subjects not immediately included in the study may be kept in the clinic until it is decided whether these subjects are to be included. If subjects are included > 48 hours after admission in the clinic on Day -1, the Day -1 assessments have to be repeated.

Table 5-2: Visit and Assessment Schedule – Part 2

Study Period	Screening	Treatment Period										FU/EOS	
		Visit 1 ¹	Visit 2		Visit 3 ²	Visit 4	Visit 5 ³	Visit 6	Visit 7	Visit 8	Visit 9	Visit 10	
Visit	Visit 1 ¹	Visit 2	Day 1	Day 2	Day 3	Day 4	Day 8 (±1)	Day 14 (±1)	Day 21 (±3)	Day 35 (±3)	Day 49 (±3)	Day 63 (±3)	Day 90 (±3)
Assessments / Study days (visit windows)	Day -42 to Day -2	Day -1 ²²											
Informed consent	X												
Eligibility criteria	X	X											
Randomization			X										
Demographics	X												
Height	X												
Weight	X	X											
BMI	X	X											
QuantiFERON® test ⁴	X												
Chest X-ray ⁵	X												
Vital signs (blood pressure, pulse rate, temperature) ⁶	X	X	X	X	X	X		X	X		X		X
General medical history	X												
RA medical history	X												
Prior and concomitant medications incl. RA medication	X												
Physical examination ⁷	X	X			X								X
Patient Global Health VAS Score		X											
DAS28-CRP and DAS28-ESR		X											
SOL-116 administration ⁸		X											
Injection site reactions ⁹			X	X		X	X						
12-lead ECG ¹⁰	X	X	X	X	X	X							X
3-lead ECG (telemetry) ¹¹			X										
Pregnancy testing ¹²	X	X									X		X
Serology	X												

Study Period	Screening	Treatment Period										FU/EOS	
		Visit 1 ¹	Visit 2		Visit 3 ²	Visit 4	Visit 5 ³	Visit 6	Visit 7	Visit 8	Visit 9	Visit 10	
Visit	Visit 1 ¹	Day -1 ²²	Day 1	Day 2	Day 3	Day 4	Day 8 (±1)	Day 14 (±1)	Day 21 (±3)	Day 35 (±3)	Day 49 (±3)	Day 63 (±3)	Day 90 (±3)
Assessments / Study days (visit windows)	Day -42 to Day -2												
Serum FSH (postmenopausal women only)	X												
Blood sampling for SOL-116 PK ¹³			X	X	X	X	X	X	X	X	X	X	
Blood sampling for immunogenicity			X ¹⁹				X		X		X		X
Blood sampling for BSSL			X ¹⁹	X	X	X	X	X	X	X	X	X	
Blood sampling for cytokine and chemokine panel			X ¹⁹	X		X			X		X		X
Blood sampling for flow cytometry and whole blood stimulation assay ¹⁴			X	X		X	X		X		X		
Blood sampling for future exploratory analysis ¹⁵			X ¹⁹	X		X	X		X		X		X
Urine drugs of abuse and cotinine screen	X	X											
Alcohol test	X	X											

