8.7.2 Dose Escalation Stopping Criteria

- One (1) or more subjects who receive SOL-116 experience a SAE which is considered to be related to the study medication.
- Two (2) or more subjects who receive SOL-116 have QTc prolongation, defined as an average absolute (regardless of baseline value) QTcF >500 msec or an increase of QTcF >60 msec above baseline, confirmed by repeated ECG after at least 5 minutes, and determined post-dose.
- Two (2) or more subjects who receive SOL-116 exhibit hypotension, defined as resting supine diastolic blood pressure <40 mmHg, an asymptomatic or symptomatic fall in systolic blood pressure to below 80 mmHg, persisting for at least 10 minutes on repeated assessment.
- Two (2) or more subjects who receive SOL-116 exhibit hypertension, defined as an increase in resting systolic blood pressure to above 180 mmHg, persisting for at least 10 minutes, or an increase in resting diastolic blood pressure to above 105 mmHg, persisting for at least 10 minutes.
- Two (2) or more subjects who receive SOL-116 exhibit tachycardia, defined as resting supine heart rate >130 beats per minute, persisting for at least 10 minutes.
- Two (2) or more subjects who receive SOL-116 exhibit symptomatic bradycardia, defined as heart rate <40 beats per minute, or asymptomatic bradycardia, defined as resting supine heart rate <30 beats per minute while awake, persisting for at least 10 minutes.
- One (1) or more subjects who receive SOL-116 fulfills Hy's law, defined as aspartate aminotransferase (AST) or alanine aminotransferase (ALT) $\geq 3 \times$ upper limit of normal (ULN) and total bilirubin $\geq 2 \times$ ULN, in the absence of a significant increase in alkaline phosphatase (ALP) and in the absence of an alternative diagnosis that explains the increase in total bilirubin (confirmed by repeating within 24 hours).
- Two (2) or more subjects who receive SOL-116 exhibit ALT, total bilirubin, or ALP $>3 \times$ ULN accompanied by significant increase in other liver function test (confirmed by repeating within 24 hours).
- Two (2) or more subjects who receive SOL-116 exhibit renal toxicity, defined as serum creatinine $\geq 1.5 \times$ ULN (confirmed by repeating within 24 hours).
- Two (2) or more subjects who receive SOL-116 exhibit hematologic toxicity, defined as one or more of the following (confirmed by repeating within 24 hours):
 - Leukocyte count $<2.5 \times 10^9/L$
 - Neutrophil count $<1.0 \times 10^9/L$

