Laboratory safety data will be summarized according to protocol scheme time point. Where applicable, change from baseline will also be calculated and summarized. Baseline is defined as the last value measured on Day -1 (or pre-dose on Day 1) The evaluations from baseline over time will be summarized as a shift table.

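### Repeat and off-schedule safety values enter no by-dose summary of measured values, and the SAP text plans no worst-post-baseline table to show them

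*SAP*

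**What the plan says.** **Exclusion rule.** SAP 7.1: "Extra measurements (such as additional visits or repeat assessments) will not be included in the descriptive statistics"; they are shown in listings only. No exception is given. For qualitative variables the same section says that "the descriptive statistics presented will be frequency counts (n) and percentages for qualitative variables", so counts fall under the rule as well as means.

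**Safety tables.** SAP 7.7.3.4 ties the laboratory summaries to the protocol's scheduled time points and adds: "The evaluations from baseline over time will be summarized as a shift table". SAP 10.2 lists shift tables for hematology, serum biochemistry and urinalysis (14.3.5.4 to 14.3.5.6). Vital signs and 12-lead ECG get summaries by time point, with counts of normal, abnormal not clinically significant (NCS) and abnormal clinically significant (CS) evaluations (SAP 7.7.3.5 and 7.7.3.6). No worst-post-baseline row is mentioned.

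**Baseline.** SAP 7.1: "baseline is defined the last value measured prior to (the first) study drug intake". For laboratory data, SAP 7.7.3.4 limits this to the last value on Day -1 or pre-dose on Day 1. For spare subjects included more than 48 hours after admission, the protocol says "the Day -1 assessments have to be repeated" (Table 5-1 footnote 17; likewise Table 5-2 footnote 22 and Table 5-3 footnote 2).

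**Sources of extra data.** Part 2 has an optional Day 3 visit, triggered by safety concerns (Table 5-2 footnote 2). The SRC may add safety time points (Protocol 8.7.1). The laboratory stopping criteria need the abnormality to be "confirmed by repeating within 24 hours" (Protocol 8.7.2).

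**The concern.** Safety is the primary endpoint in all three parts (Protocol 8.1.1) and the SAP plans no inference, so the descriptive tables carry the conclusions. Leaving unscheduled values out of by-visit means is ordinary practice, because such values distort the mean at a visit. Leaving them out of the shift counts as well, with nothing in their place, means that no table by dose group uses all the post-dose measurements. A dose-related pattern of findings each judged not clinically significant could then be seen only by reading listings across cohorts.

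Two smaller gaps sit beside this. The SAP does not say whether the exclusion touches the choice of baseline, and it does not say whether the optional Day 3 visit or an SRC-added time point is an additional visit in the sense of the rule.

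**Working it through.** The documents state no figure on this point, so there is none to reproduce. The check is a reading of the rules case by case, then arithmetic for scale.

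**1. What the rules do with a post-dose laboratory value**

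| Case | By-visit and shift tables | Elsewhere |
|---|---|---|
| Scheduled value abnormal, repeat confirms | Scheduled value counted | Repeat in listings |
| Scheduled value abnormal, repeat normal | Unconfirmed abnormality stays counted | Repeat in listings |
| Abnormal only off schedule, NCS | Not counted | Listings; 14.3.4 if out of range |
| Abnormal only off schedule, CS | Not counted | Listings; adverse event tables (Protocol 8.3.4.11, SAP 7.7.3.3) |

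Only the third case is missing from every by-dose table. The second case leans the other way and leaves too much abnormality in the table. For ECG and vital signs the logic is the same. Clinically significant findings become adverse events (Protocol 8.3.4.4 and 9.1.1), no shift table is planned, and the effect falls on the by-time-point counts and on the minimum and maximum.

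**2. Weight of one subject, 1/n** (group sizes from Protocol 8.2; the optional sixth cohort was not run; placebo pooled within part under SAP 7.1)

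- Active dose level: n = 6, 1/6 = 16.7 points
- Part 1 placebo: n = 5 × 2 = 10, 1/10 = 10 points
- Part 2 placebo: n = 2, 1/2 = 50 points
- Part 3 placebo, if both cohorts run: n = 2 × 2 = 4, 1/4 = 25 points

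A subject in the third case thus shows as 0/6 instead of 1/6. This is the weight of any one subject in any table, not an estimate of how often the case arises.

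**3. How often: assumption only.** If a share p of subjects is affected, independently, the chance of at least one in a group of 6 is 1 − (1 − p)^6. For p = 5%, 10% and 20% this gives 0.265, 0.469 and 0.738. The documents give no p, either for off-schedule abnormalities or for pre-dose repeats.

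**4. Baseline.** In all parts the scheduled Day 1 12-lead ECGs are 1 and 4 hours post-dose, and most routine safety laboratory tests have their last scheduled pre-dose sample on Day -1. A repeated Day -1 assessment therefore decides the baseline for these. Vital signs and BSSL have a Day 1 pre-dose value in every part and are not affected. If two programmers chose different baselines for one subject and these differed by d units, the group mean change would move by d/n. With n = 6 that is 0.83, 1.67 or 3.33 for d = 5, 10 or 20 (assumed values).

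**5. Day 3 in Part 2.** Table 5-2 schedules vital signs and 12-lead ECG at this visit but no routine safety laboratory tests. Its classification therefore matters for ECG and vital signs, not for the shift tables.

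**The case against.** The strongest reply is that little of importance is lost. Clinically significant findings become adverse events whether or not the visit was scheduled, and are tabulated by system organ class, intensity and relationship. Table 14.3.4 lists every out-of-range laboratory value with its NCS or CS rating, and a cohort of 8 can be read line by line. The scheduled value that prompts a repeat remains in the tables. Protocol 10.4 asks only for summaries at each time point and requires no shift table, so the SAP already goes further. The stopping criteria govern SRC decisions, not report tables. Full table layouts are in a separate mock-table document, so a worst-value row may exist there.

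All of this stands, and it limits the point. It does not remove it. The adverse event route depends on the investigator's judgement of significance, the SAP itself tabulates NCS evaluations, and a listing gives no count by dose group.

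Three stronger readings are tempting, and the documents do not support them:

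- A reader might infer that SAP 7.1 contradicts itself on baseline. It does not. One rule says which records are summarized, the other picks a reference value, and the last pre-dose value plainly covers a pre-dose repeat. What is missing is a sentence saying so.
- A reader might infer that the tables understate abnormality. The direction is not fixed, because a refuted scheduled abnormality remains counted.
- A reader might infer that the most safety-relevant values are hidden. The clinically significant ones reach the adverse event tables.

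**Conclusion.** The point holds as a low-cost improvement to the safety summaries. Followed as written, SAP 7.1 keeps repeat and additional-visit values out of every by-dose summary of measured values, including the laboratory shift tables, and nothing in the SAP text compensates. The loss is confined to abnormal values that are seen only off schedule and judged not clinically significant. Each such subject changes a shift percentage by 16.7 points in an active group of 6 and by 10 points in pooled Part 1 placebo. Neither the frequency nor the net direction can be derived from the documents.

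This rests on the SAP text alone, without the mock tables, and on reading shift-table counts as descriptive statistics, which the wording of SAP 7.1 supports. The baseline and visit-classification gaps are matters of clarification.

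**What to change.** 1. Keep the by-visit summaries on scheduled values.
2. Add a worst-post-baseline row to the hematology, biochemistry and urinalysis shift tables, and a worst-post-baseline evaluation count for 12-lead ECG and vital signs. Use all post-dose values, including unscheduled and repeat ones, with the order normal, abnormal NCS, abnormal CS.
3. State in SAP 7.1 that the exclusion does not apply to deriving baseline, so that a valid pre-dose repeat, such as the repeated Day -1 assessment of a spare subject, is the baseline. Align the wording of 7.1 and 7.7.3.4.
4. State that the optional Part 2 Day 3 visit and SRC-added time points are not extra measurements in the sense of SAP 7.1.

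The cost is a few sentences and one derivation per table. Worst-value counts run higher than single-visit counts in every group, so they must be read against placebo. They also still count a scheduled abnormality that a repeat refutes, so a footnote should refer the reader to the listing for the repeat result.

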7.2 Incomplete and Missing Data

Subjects who drop-out might be replaced but only upon mutual agreement between the Investigator and the Sponsor unless withdrawal is due to adverse event (AE). The replacing subject will receive the same treatment as was assigned to the subject whom he/she replaces.

No imputation will be performed on missing data. All analyses will be performed on data available at the time point considered. In summary tables, the number of subjects with missing data will be presented unless otherwise specified. In calculation of percentages, subjects with missing data will not be considered in numerator or denominator unless otherwise specified.

For the safety evaluation, subjects with missing data are included until their last assessment in both listings and tables.

In listings, dates will be presented as exported from the database, also in case of partial dates.

7.3 Demographic and Baseline Characteristics

Descriptive tabulations of the screening data for demographics will be made. Demographic data of continuous variables (age, height, weight, and body mass index (BMI)) as well as qualitative demographic characteristics (sex, ethnicity and race) will be presented appropriate descriptive statistics. Individual subject listings of demographic data will be provided.

Previous and concomitant medications will be coded according to the latest version (version 2022 or higher) of the world health organization (WHO) drug code and the anatomic therapeutic chemical (ATC) class code. Concomitant medications will be summarized by tabulating the number and percentages of subjects treated.

Based on the status dataset (see [Section 6.2](#)), a summary of all screened/ randomized, treated and completed subjects by treatment groups will be given ("subject disposition") for all-treated set.

Other baseline subject characteristics including medical history (MH), physical examination, previous medication, inclusion/exclusion checklist, alcohol breath test, urine drug screen, urine cotinine screen, serology, anti-CCP antibody, and QuantiFERON® test will only be listed.

MH data will in addition be coded with the latest version of the medical dictionary for regulatory activities (MedDRA) coding system used during the clinical conduct of the study: this is version 25.1 or higher. The SAS programmer or Data Manager of the study will add the coding (using the MedDRA system and SAS) to the MH descriptions extracted from the database.

Distributions of these parameters will be compared between the treatment groups only descriptively. No statistical inference will be performed.

7.4 Study Subjects and Conduct

The status of the subjects will be given in a summary table by dose level:

- the number of subjects screened
- the number of subjects randomized
- the number of subjects receive study drug
- the number of subjects which completed the study
- the number of subjects for the non-completion reason
- the number of subjects in the all-treated set
- the number of subjects in the safety set
- the number of subjects in the immunogenicity set
- the number of subjects in the per-protocol set
- the number of subjects in the PD (exploratory) set

Subject eligibility and the criteria not met will be listed in the Subject Eligibility Not Met listing. Subject disposition, completion and the reasons for discontinuation will be listed in the Subject Disposition (Complete Status) listing. The reasons for exclusion from all-treated set, safety set, immunogenicity set, per-protocol set, and PD (exploratory) set will be listed in the Subject Excluded from the Analysis.

7.5 Immunogenicity Analyses

7.5.1 Immunogenicity Parameters

The immunogenicity parameters to be presented are:

- Development of anti-drug antibodies (ADA). If confirmed ADA positive, the following may be determined:
 - Estimation of ADA titers
 - Neutralizing capacity
 - Isotype
 - Epitope map

The immunogenicity parameters will be summarized by using descriptive statistics of absolute values for each time point. Where applicable, change from baseline will also be calculated and summarized.

The immunogenicity set will be used for analyses.

7.6 Exploratory Analyses

7.6.1 Exploratory Parameters

The exploratory parameters to be presented are:

- BSSL concentration
- Inflammatory biomarkers (except BSSL): CRP, ESR for all subjects/patients, and S-calprotectin and hsCRP (only RA patients)

The exploratory parameters will be summarized by using descriptive statistics of absolute values for each time point. Where applicable, change from baseline will also be calculated and summarized.

Exploratory data-driven analyses can be performed with the caveat that any statistical inference will not have any confirmatory value.

The PD (Exploratory) set will be used for analyses. Also, the Per-protocol (PP) set and the “all-treated set” will be used (see CSP section 10.2).

7.7 Safety Tolerability Evaluations

7.7.1 General Considerations

Safety evaluations will be conducted at screening, at clinic check-in, periodically throughout study conduct, and at follow-up evaluation. See Table 5-1, Table 5-2, and Table 5-3 in the CSP for the details of evaluation time points. All safety and tolerability assessments, including but not limited to adverse events, clinical laboratory assessments including hematology, serum biochemistry, coagulation and urinalysis, vital signs, 12-lead ECG and 3-lead ECG.

